3.3 Exploratory Objectives

Part A – CX-2009 Monotherapy: Every 21-Day Dosing Regimen

The exploratory objectives of Part A are to determine the following in subjects treated with CX-2009 every 21 days:

- Explore potential predictive markers associated with CX-2009 clinical activity such as CD166 expression in tumor specimens prior to and while receiving treatment; and
- Characterize the protease activity in optional pretreatment tumor biopsies and activation of CX-2009 in optional on-treatment tumor biopsies and peripheral blood.

Part A2 – CX-2009 Monotherapy: Every 21-Day Dosing Regimen

The exploratory objectives of Part A2 are to determine the following in subjects treated with CX-2009 every 21 days:

- Evaluate the relationship between CX-2009 dose and exposure, exploratory biomarkers, safety, and efficacy of CX-2009 as monotherapy in subjects with selected advanced or recurrent solid tumors with demonstrated high tumor expression of CD166; and
- Explore potential predictive markers associated with CX-2009 clinical activity such as CD166 expression in tumor specimens from subjects with demonstrated high tumor expression of CD166 while receiving treatment.

Part B – CX-2009 Monotherapy: Every 21-Day Dosing Regimen

The exploratory objectives of Part B are to determine the following in subjects treated with CX-2009 every 21 days:

- Explore potential predictive markers associated with CX-2009 clinical activity such as CD166 expression in tumor specimens prior to and while receiving treatment from subjects with demonstrated high tumor expression of CD166;
- Measure the intact and activated CX-2009 in on-treatment tumor biopsies and peripheral blood; and
- Characterize the protease activity in pretreatment tumor biopsies.

Part C1 – CX-2009 Monotherapy: Every 14-Day Dosing Regimen

The exploratory objectives of Part C1 are to determine the following in subjects treated with CX-2009 every 14 days:

- Explore potential predictive markers associated with CX-2009 clinical activity such as CD166 expression in tumor specimens prior to and while receiving treatment; and
- Characterize the activation of CX-2009 in optional on-treatment tumor biopsies and peripheral blood.

4. Study Methods

4.1 Overview of Study Design

This is a Phase 1-2, open-label, multicenter, dose-finding, and proof of concept study for CX-2009 as monotherapy in subjects with advanced solid tumors in selected indications.

The study (as of Protocol Amendment 06) has 7 parts, as described below (Figure 1). Since the enrollment ended after Parts A, A2, B, and C1, the description is limited to those parts.

Part A: Dose escalation and determination of MTD/RP2D of the CX-2009 monotherapy every 21-day dosing regimen ($n \leq 79$: based on actual enrollment of initial cohorts and assumption of remaining cohorts and up to 38 total subjects enrolled into the mTPI-2 design cohort): This part will initiate with accelerated dose titration in 1 single-subject cohort (0.25 mg/kg [mpk], adjusted ideal body weight [AIBW]), followed by a standard 3+3 design to determine the MTD, and end in a mTPI-2 design cohort with up to 38 subjects with demonstrated high CD166 expression to determine the RP2D. The mTPI-2 design is a rule-based design similar to the 3+3 design and allows dose escalation/de-escalation. It is assumed to be of similar accuracy in determining the optimal dose as model-based design (Ji et al, 2007) but allows a more flexible sample size. To understand the statistical rationale for the design, please refer to Section 9 and Appendix C of the CTMX-M-2009-001 Protocol Module.

[figure not shown]
Part A2: Additional enrollment into previously cleared CX-2009 monotherapy dose levels from Part A ($n \leq 42$) for every 21-day dosing regimen: This part will help inform selection of the optimal MTD/RP2D by requiring measurable disease, mandating biopsies to assess Probody therapeutic CX-2009 performance, and selecting for confirmed high CD166 expressing tumors by IHC. Additionally, the relationship between dose/exposure and safety as well as antitumor activity will further enhance MTD/RP2D selection by including more subjects for safety evaluation and selecting for confirmed high CD166 expression in tumors by IHC in Part A2. Part A2 will interrogate dose levels beginning at 4 mg/kg and up to the MTD/RP2D determined in Part A. The expression of CD166 will be evaluated on archival samples using a Clinical Laboratory Improvement Amendments of 1998 (CLIA)-validated IHC assay.

Part B: Dose expansion (proof of concept) at the MTD/RP2D of CX-2009 monotherapy every 21-day dosing regimen with proof of concept in selected tumor types (maximum $n \leq 200$): This part will explore efficacy of CX-2009 by requiring measurable disease and selecting for confirmed high CD166 expressing tumors. Part B will enroll up to a total of 40 subjects in each of 1 or more of the 5 tumor types listed in Table 4 in the CTMX-M-2009-001 Protocol Module. Part B will only be initiated if, after the review of dose escalation data (Parts A and A2), an every 21-day dosing regimen is considered for further development.

Part C1: Dose escalation and determination of the MTD/RP2D of the CX-2009 monotherapy every 14-day dosing regimen in subjects with high CD166 expression ($n \leq 18$): The highest dose level tested in this clinical study for CX-2009 was 10 mg/kg administered every 21 days, which successfully cleared the DLT evaluation period. The every 14-day dosing regimen equivalent of 10 mg/kg administered every 21 days is ≥ 7 mg/kg. In order to provide an additional margin of safety coverage for Part C1, the starting dose will be 6 mg/kg, AIBW, administered every 14 days. The mTPI-2 design will be used to determine the MTD/RP2D for this schedule. The following cohort's dose will be increased according to the defined dose escalation

rules to 8 mg/kg and then to 10 mg/kg based upon the observed safety tolerability profile as determined in consultation with the SRC. Prior to a dose escalation, a minimum of 3 evaluable subjects must be assessed per the mTPI-2 algorithm (Figure 6 from the CTMX-M-2009-001 Protocol Module). The maximum dose level that will be tested in Part C1 will be 10 mg/kg. Part C1 will include up to 18 subjects. Subjects will be selected from the following indications: BC, NSCLC, or HNSCC.

Figure 1: Study Design Schema: Parts A, A2, and B (every 21-day Dosing Regimen)

^a Part A eligible tumor types: BC, CRPC, NSCLC, OEC, EC, HNSCC, and CCC.

^b Part A2 restricted to subjects with BC, NSCLC, OEC, EC, and HNSCC.

[figure not shown]
^c Part A mTPI-2 cohort eligible tumor types: BC, NSCLC, and HNSCC.

^d Part B eligible tumor types: TNBC, HR-positive/HER2-negative BC, NSCLC, OEC, and HNSCC.

Note: Parts A (mTPI-2 cohort only), A2, and B will enroll subjects with confirmed high CD166 expressing tumors.

BC = breast cancer; CCC = cholangiocellular carcinoma; CRPC = castrate-resistant prostate carcinoma; EC = endometrial carcinoma; HER2 = human epidermal growth factor receptor 2; HNSCC = head and neck squamous cell carcinoma; HR = hormone receptor (ie, estrogen and/or progesterone); mpk = mg/kg; MTD = maximum tolerated dose; mTPI-2 = modified toxicity probability interval 2; NSCLC = non-small cell lung carcinoma; OEC = ovarian epithelial cancer; RP2D = recommended Phase 2 dose; TNBC = triple negative breast cancer.

Figure 2: Study Design Schema: Parts C1 and C2 (every 14-day Dosing Regimen)

^a Part C1 eligible tumor types: BC, NSCLC, and HNSCC.

^b Part C2 eligible tumor types: TNBC, HR-positive/HER2-negative BC, NSCLC, OEC, and HNSCC.

Note: Parts C1 and C2 will enroll subjects with confirmed high CD166 expressing tumors.

BC = breast cancer; OEC = ovarian epithelial cancer; HER2 = human epidermal growth factor receptor 2; HNSCC = head and neck squamous cell carcinoma; HR = hormone receptor (ie, estrogen and/or progesterone); NSCLC = non-small cell lung carcinoma; mpk = milligram per kilogram; MTD = maximum tolerated dose; RP2D = recommended Phase 2 dose; TNBC = triple negative breast cancer.

4.2 Subject Eligibility and Enrollment

[figure not shown]
At the time of the sponsor decision to stop enrollment into the study, there were 99 subjects enrolled and treated in the study: 37 in Part A, 39 in Part A2, 10 in the mTPI-2 cohort, 3 in Part B, and 10 in Part C1.

4.3 Study Periods and Follow-Up

The study is divided into periods with associated evaluations and procedures that must be performed at specific time points. The schedule of procedures in Appendix B of the CTMX-M-2009-001 Protocol Module summarizes the frequency and timing of efficacy, safety, and other study measurements. Refer to the Common Core Document for a description of each procedure.

As with any Phase 1 study, an individual subject's participation in the study is difficult to predict. It is estimated that average treatment will last approximately 6 months, followed by Follow-Up contact every 3 to 6 months for another 1 to 2 years, or as long as the subject remains alive (Figure 3).

Figure 3: Study Periods

Notes: An EOT Visit will be conducted 30 days (± 7 days) after the last infusion of study treatment. Follow-Up: If subject has not had progression, imaging assessments will continue until progression is documented. If subject had documented progression, the subject will continue in survival Follow-Up Visits every 3 months (± 14 days) after the EOT Visit for 1 year and then every 6 months (± 14 days) (this may be by telephone), or until death. Subsequent cancer treatment will be collected. Survival Follow-Up will be done every 3 months (± 14 days) as described above.

DLT = dose-limiting toxicity; EOT = end of treatment; IV = intravenous; q14 = every 14; q21 = every 21.

Following the completion of study treatment, subjects with progressive disease per RECIST v1.1 as measured by investigator assessment, will return for an end of treatment (EOT) Visit and then enter the Follow-Up Period for monitoring of survival. Subjects who for other reasons stop study drug treatment and subjects with stable disease, confirmed partial response, or confirmed complete response will enter the Follow-Up Period for monitoring of DOR and PFS.

The study will be completed approximately 2 years from the date the last subject is enrolled or when the last subject has completed treatment and the last Follow-Up Visit.

The EOT Visit will be conducted 30 days (± 7 days) after the last infusion of CX-2009. Once a subject experiences progressive disease, they will continue to be monitored for survival. All subjects will return for Follow-Up Visits every 3 months after the EOT Visit for 1 year and then every 6 months to ensure resolution of toxicities and as applicable, confirm negative pregnancy status. During the EOT Visit, subjects will be followed for resolution of toxicity. Women of childbearing potential will undergo monthly pregnancy testing while on study drug and through 50 days after the last dose of CX-2009, or 6 months after the last dose of CX-072, as applicable, whichever is later. Thereafter, Follow-Up Visits will be conducted for survival information and may be performed by telephone.

4.4 Administration of the study drug

Treatment will be administered on an outpatient basis, with inpatient admission as needed for any treatment or monitoring outside of clinic hours or for management of significant acute toxicity.

CX-2009 will be administered at a dosage of 0.25, 0.5, 1, 2, 4, 5, 6, 7, 8, 9, 10 mg/kg/dose (Adjusted Ideal Body Weight should be applied [Appendix F of the CTMX-M-2009-001 Protocol Module]).

4.5 Discontinuation of Subjects from Treatment

Subject MUST discontinue the study drug for any of the following reasons:

- The subject experiences clinically significant or confirmed (RECIST v1.1) disease progression (or irRECIST in Parts D1 and D2);
- The subject is unwilling or unable to adhere to the Module;
- The subject withdraws consent or is lost to follow-up;
- The subject experiences an intercurrent illness that prevents further administration of study drug;
- The subject requires new/other anti-cancer treatment;
- The subject experiences a DLT or an adverse event related to study drug which precludes further administration of the study drug;
- The subject experiences a prolonged treatment delay (as defined in Section 5.5.4 of the CTMX-M-2009-001 Protocol Module);
- The subject becomes pregnant, either prior to the first dose of study drug or at any time during treatment;
- In the Investigator's judgment, the subject should discontinue treatment;
- Death of the subject; or
- The Sponsor terminates the study.

Subjects who discontinue study drug administration, for reasons other than TRAEs, may be replaced to ensure the minimum number of subjects required for DLT evaluation is enrolled. Subjects who have enrolled in the study and have withdrawn prior to receiving the first dose will be designated as screen failures. The reason for subject withdrawal must be documented in the electronic case report form (eCRF).

5. Study Endpoints

5.1.1 Primary Safety Domains

Incidence and nature of DLTs, adverse events, serious adverse events, and adverse events of special interest, as well as physical examinations, vital sign measurements, triplicate electrocardiograms, clinical laboratory evaluations, and treatment discontinuation due to toxicity will be evaluated for safety assessment.

5.1.2 Primary Efficacy Endpoint

The primary criteria for defining evidence of anti-cancer activity and also for management of subject care will be a clinical response as defined by RECIST (Version 1.1). ORR is the primary efficacy endpoint and ORR is defined as the proportion of subjects with complete response (CR) or partial response (PR) on two consecutive tumor assessments at least 4 weeks apart according to RECIST (RECIST v1.1).

5.1.3 Secondary Efficacy

Efficacy in this study will be explored in subjects treated with CX-2009 as monotherapy on the basis of:

- TTR;
- DOR;
- PFS; and
- OS.

6. Data Capture and Processing

Electronic data capture will be used for the study. Data will be recorded on source documentation at each study location and entered into the eCRF electronically by the study center personnel for each study subject. Data collected on each subject will be documented on the appropriate eCRF. Completed eCRFs are to be reviewed and electronically signed by the Investigator or his/her designee.

7. Analysis and Reporting

7.1 Interim Analyses

No formal interim analysis is planned.

Administrative interim analyses on safety and efficacy or on PK, immunogenicity, and selected biomarkers may be performed several times prior to completion of the study in order to facilitate program decisions and to support study presentations or publications.

7.1.1 Safety Review Committee (SRC)

A Safety Review Committee (SRC) has been established for the study. The SRC will consist of selected Investigators from the trial and representatives from CytomX who will review on a regular basis, approximately monthly, the cumulative safety data from each cohort in the study in order to:

- Approve dose escalation to the next cohort in Part A, Part A2, or Part C1 of the study;
- Recommend modifications to the dose or schedule as it pertains to subject safety; or
- Recommend modifications to the protocol related to subject oversight (e.g., additional safety monitoring, changes to inclusion/exclusion criteria).

The SRC will review safety data in conjunction with the Statistical and Medical Groups from CytomX.

7.1.2 Data Safety Monitoring Board (DSMB)

A Data Safety Monitoring Board (DSMB) has been established for the study. The DSMB will review table summaries and listings provided by IDDI in conjunction with the Statistical and Medical Groups from CytomX. Tables including, but not limited to, subject disposition, demographics and baseline characteristics, drug exposure, and AEs will be provided. Details on the DSMB are provided in Appendix D of the CTMX-M-2009-001 Protocol Module and in a separate DSMB charter. The DSMB will make recommendations to the Sponsor, who will make ultimate decisions regarding study alteration or discontinuation.

7.1.3 Final Analysis

Data summaries, figures, and listings will be prepared as identified in this SAP following database lock.

8. Sample Size Determination

Enrollment into the study was stopped by the sponsor with 99 subjects enrolled and treated across Parts A, A2, B, and C1. The previously planned sample size was a maximum of 563 subjects enrolled across Parts A, A2, B, C1, C2, D1, and D2. No subjects were enrolled in Parts C2, D1, or D2 for this study.

Refer to the CTMX-M-2009-001 Protocol Module for explanation on the original sample size calculation and statistical assumptions related to the design of the study.

9. Definition of Populations

Analysis populations for tabulations and figures are defined below for the following populations: safety analysis population (SP) and the response evaluable population (REP). Subject disposition will be based on the number of subjects providing signed informed consent.

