1.3.4.1 Summary of CX-2009 Clinical Safety

A total of 92 subjects treated with CX-2009 had available safety data. All but 6 subjects received CX-2009 once every 21 days at doses ranging from 0.25 mg/kg to 10 mg/kg. Six subjects received CX-2009 once every 14 days at a dose of 6 mg/kg. Please refer to the Investigator's Brochure (IB) for the most up-to-date information.

Overview of Treatment-emergent Adverse Events

Approximately 91.3% (84 of 92) of subjects had adverse events (AEs) that were judged by the Investigator to be related to study treatment. Forty-two (45.7%) had ocular toxicity that was related to CX-2009, with symptoms similar to other DM4 ADCs.

Twenty-six (28.3%) subjects experienced peripheral neuropathy related to CX-2009. The majority (13/26) had events that were Grade 1. Five subjects had Grade 3 peripheral neuropathy related to CX-2009.

Twenty (21.7%) subjects experienced infusion-related reactions (IRRs), the majority of which were Grade 1 or 2 (1 subject had a Grade 3 IRR). A previous analysis noted that the majority of subjects who had an IRR at the first infusion cycle, did not experience recurrence at subsequent infusions when premedication was administered.

Treatment-related SAEs and Treatment-related AEs Grade 3 or Higher

Eleven (12.0%) subjects experienced treatment-related serious adverse events (SAEs). Thirty-four (37.0%) subjects experienced Grade 3/4 treatment-related adverse events (TRAEs), including 10 with ocular toxicity (n = 8 Grade 3, n = 2 Grade 4) and 5 with peripheral neuropathy (all Grade 3).

There was 1 death related to study treatment according to Investigator's assessment.

Refer to the most recent version of the CX-2009 IB for the most updated and complete safety data.

Dose-Limiting Toxicities

One DLT was observed in Part A (8 mg/kg every 21 days); a Grade 3 event of vomiting that resolved (22 subjects were treated at this dose and schedule). No DLTs were observed at 9 and 10 mg/kg in 9 and 8 subjects, respectively.

Three DLTs were reported in 2 out of 5 evaluable subjects who received CX-2009 at a dose of 6 mg/kg every 14 days (Part C1) including a Grade 3 increased aspartate aminotransferase (AST) and a Grade 3 increased alanine aminotransferase (ALT) in 1 subject, and a Grade 3 peripheral neuropathy in another subject.

Treatment-emergent Adverse Events Related to CX-2009 at the Every 21-day Monotherapy RP2D of 7 mg/kg

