The mTPI-2 cohort will evaluate up to 5 dose levels based on DLT events and TRAEs leading to treatment delay or discontinuation, including events of special interest (eg, ocular toxicity and peripheral neuropathy). As events of special interest have been observed at later time points, TRAEs leading to treatment interruption (ie, missed dose) or treatment discontinuation will be evaluated over an extended interval that encompasses the first 3 infusions (42 days). An event for the mTPI-2 cohort is defined as either a DLT or a TRAE leading to treatment interruption (ie, missed dose) or treatment discontinuation. The decision-making tables for the mTPI-2 cohort are provided in [Appendix C](#).

For dosing, AIBW should be applied ([Appendix F](#)).

Subjects may be permitted individual dose escalations to previously cleared dose levels following consultation with the Medical Monitor.

The DLT assessment period for dose escalation is 21 days.

Subjects in Part A who discontinue study drug administration for reasons other than DLTs may be replaced to ensure the minimum number of subjects required for DLT evaluation is enrolled.

As of November 2019, the RP2D for CX-2009 administered every 21 days was determined to be 7 mg/kg. For justification of this dose, refer to Sections [1.3.4.1](#) and [5.2](#).

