9.1 Populations

For assessment of MTD/RP2D, the population will be based on subjects who are evaluable for DLT determination (a “DLT-evaluable” subject is defined as having received at least 1 dose of CX-2009 (or CX-2009 and CX-072) and completed the full DLT observation period (either 21 or 28 days depending on the schedule) or a subject who has withdrawn from the study drug due to a drug-related toxicity. Subjects who are not DLT evaluable may be replaced in the cohort.

For assessment of efficacy (Parts B, C2, D2 and E2), subjects must have undergone at least 1 on-study imaging assessment. Subjects who die prior to his/her first on-study scan will not be counted as evaluable for this assessment.

The efficacy evaluable group for Parts D2 and E2 will include only those subjects who are determined to be PD-L1 positive.

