9.1 Safety Analysis Population (SP)

The safety analysis population includes all enrolled subjects who receive at least one dose of study drug. The safety analysis population is used for evaluating subject characteristics, treatment administration, safety endpoints and efficacy analyses related to PFS and OS.

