- SAEs related to CX-2009
- SAEs related to CX-2009 with CTCAE Grade 3 or higher
- TEAE of Special Interest
- DLT AEs
- Deaths

If there are no subjects who meet the criteria for any of these listings, the listing will be generated and will contain a statement, "No <criteria> were reported." for example, if there are no deaths on study, the statement would be "No deaths were reported."

Overall AE summary tables will each be prepared by dose level, by cancer type, and by Breast Cancer cohort (TNBC, HR+/HER2-, HER2+), and will include the number and percentage of subjects with reports of:

- TEAEs
- TEAEs related to CX-2009
- TEAEs with CTCAE Grade 3 or higher
- TEAEs with CTCAE Grade 3 or higher related to CX-2009
- TEAEs classified as infusion reactions
- TEAEs classified as infusion reactions with CTCAE Grade 3 or higher
- TEAEs leading to study drug discontinuation
- TEAEs leading to study drug discontinuation and related to CX-2009

- Dose-Limiting Toxicities (DLTs)
- Treatment-emergent SAEs (TESAEs)
- TESAE related to CX-2009
- TEAEs leading to death
- TEAEs leading to death and related to CX-2009
- TEAEs of Special Interest
- TEAEs of Special Interest with CTCAE Grade 3 or higher
- TEAEs of Ocular Toxicity related to CX-2009
- TEAEs of Ocular Toxicity related to CX-2009 with CTCAE Grade 3 or higher
- TEAEs of Neuropathy related to CX-2009
- TEAEs of Neuropathy related to CX-2009 with CTCAE Grade 3 or higher
- TEAEs of Hepatic Disorders related to CX-2009
- TEAEs of Hepatic Disorders related to CX-2009 with CTCAE Grade 3 or higher

This overall AE summary table will also be produced for the DSMB meetings. TEAEs categorized as Ocular Toxicity, Neuropathy, or Hepatic Disorders will be defined based on a search list provided by CytomX prior to database lock.

Only TEAEs (excluding unrelated, fatal AEs with PT="Malignant neoplasm progression") will be included in the AE summaries and be tabulated by MedDRA SOC and PT within part and dose cohort. Tables presenting summaries of frequencies and percentages of subjects reporting at least one TEAE within each MedDRA SOC and PT by dose level and by cancer type will be provided for TEAEs and TESAEs as follows:

- All TEAEs
- Grade 3 or higher TEAEs
- TEAEs related to CX-2009
- TEAEs related to CX-2009 by maximum severity grade
- Grade 3 or higher TEAEs related to CX-2009
- Grade 3 or higher TEAEs related to CX-2009 by maximum severity grade
- TEAEs leading to study drug discontinuation
- TEAEs leading to death

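### The SAP has no DLT-evaluable population, so DLT rates would be reported over all treated subjects (2/6 instead of 2/5 at 6 mg/kg every 14 days), and the protocol's second monitored safety rate is not summarised

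*SAP*

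**What the plan says.** The primary objective of Parts A and C1 is the safety profile, the MTD/RP2D and the DLTs (Protocol 2.1.1 and 2.1.4; SAP 3.1). Protocol 9.1 fixes the population: "For assessment of MTD/RP2D, the population will be based on subjects who are evaluable for DLT determination". Protocol 3.1 and 9.1 define such a subject as one who received at least one dose and either completed the 21- or 28-day DLT period or withdrew because of drug-related toxicity.

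SAP Section 9 names two populations only: "Analysis populations for tabulations and figures are defined below for the following populations: safety analysis population (SP) and the response evaluable population (REP"). On the first of these, SAP 9.1 states that "The safety analysis population includes all enrolled subjects who receive at least one dose of study drug", and then that "The safety analysis population is used for evaluating subject characteristics, treatment administration, safety endpoints and efficacy analyses related to PFS and OS". SAP 5.1.1 opens its primary safety domains with "Incidence and nature of DLTs, adverse events, serious adverse events, and adverse events of special interest". SAP 12.1 puts "Dose-Limiting Toxicities (DLTs") as a row in the overall AE summary, given as number and percentage of subjects by dose level. SAP 10.1 makes 6 mg/kg every 14 days its own dose group.

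The protocol monitors two rates in the Part A mTPI-2 cohort and in Part C1 (Sections 3.2 and 3.6): DLTs, with a limit of 30%, and delayed AEs leading to interruption or discontinuation in the first 6 weeks, with a limit of 20%. For the Part A mTPI-2 cohort, Section 3.2 also defines a composite: "An event for the mTPI-2 cohort is defined as either a DLT or a TRAE leading to treatment interruption (ie, missed dose) or treatment discontinuation", with the treatment-related AEs counted over the first three infusions (42 days).

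**The concern.** A subject who leaves early for a reason other than toxicity has not been observed for the full DLT window. The protocol therefore leaves that subject out of the denominator and allows replacement. Under the SAP the same subject stays in the denominator and contributes no DLT, so any dose with both a DLT and a non-evaluable subject shows a rate that is too low. DLTs are part of the primary objective, and SAP Section 1 says these analyses will support the SRC, the DSMB, publications and FDA submissions.

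The second gap concerns the delayed events. SAP 12.1 tabulates TEAEs leading to discontinuation, overall and related, with no time window, and has no row for AEs leading to interruption. A reader of the planned tables could not tell whether a dose met the 20% limit.

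**Working it through.** **Inputs.** Protocol 1.3.4.1, data to 30 November 2019: "Three DLTs were reported in 2 out of 5 evaluable subjects who received CX-2009 at a dose of 6 mg/kg every 14 days". The same section gives six subjects treated at that dose and schedule, and Protocol 5.2.1.1 repeats six enrolled and 2 of 5 evaluable with a DLT. So x = 2 subjects with a DLT, E = 5 evaluable, T = 6 treated. The three DLTs fall in two subjects, so the subject count is 2.

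**Rates.**
- Protocol basis: x/E = 2/5 = 40.0% (exact 95% CI 5.3% to 85.3%).
- SAP basis: x/T = 2/6 = 33.3% (exact 95% CI 4.3% to 77.7%).
- Difference: 40.0 − 33.3 = 6.7 percentage points. The reported rate is E/T = 5/6 of the protocol-basis rate.
- Against the 30% limit: 10.0 points above on the protocol basis, 3.3 points above on the SAP basis. Both exceed it.

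**Decision tables in Appendix C.** Figure 6 (target 30%) prints D at 2/5 and S at 2/6. I reproduced these two cells using intervals of width 0.10 around the target band 0.25 to 0.35, and a Beta(1,1) prior, which is an assumption because the protocol does not state one.
- 2/5: posterior Beta(3,4), mode 2/5 = 0.40. The interval with most mass is 0.35 to 0.45, so D. P(rate > 0.30) = 0.744.
- 2/6: posterior Beta(3,5), mode 2/6 = 0.33. The interval with most mass is 0.25 to 0.35, so S. P(rate > 0.30) = 0.647.

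With a 0.95 exclusion threshold (also assumed), rows 0 to 5 of Figure 6 agree in every cell except 2 of 2, which is printed D and computed DU and has no bearing here. Figure 7 (target 20%) gives D for both 2/5 and 2/6.

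**Other doses.** Protocol 1.3.4.1 reports one DLT at 8 mg/kg every 21 days among 22 treated, and none at 9 or 10 mg/kg (9 and 8 subjects). A zero numerator cannot be diluted. At 8 mg/kg the evaluable number is not given. The rate is 1/22 = 4.5% if all were evaluable, and 1/11 = 9.1% even if only half were, so that conclusion is insensitive.

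**Delayed events, side by side.** The protocol counts treatment-related AEs causing a missed dose or discontinuation within 6 weeks. The nearest SAP row is related TEAEs leading to discontinuation at any time. Action taken appears only in the AE listings and in the profile tables for infusion reactions, ocular toxicity, neuropathy and hepatic disorders. Neither the interruption component nor the 42-day window is summarised. The documents give no counts for these events, so no rate can be computed.

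**The case against.** The best defence is that no dose decision is read from this table. Enrollment had stopped, the final tables follow database lock, and dose decisions lay with the sponsor in consultation with the SRC. The SAP still refers to evaluable subjects in its Part C1 design text (4.1) and to replacement for DLT evaluation (4.5). Protocol 9.2 lets the SAP override the Core but does not say that it overrides Section 9.1 of the Module. The DLT denominator is also not printed in SAP 12.1; it is inferred from the assignment of safety endpoints to the safety population. All of this stands. It limits the consequence but does not supply the missing population, and the only rule the SAP states leads to all treated subjects.

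A reader might infer from the S against D in Figure 6 that the SAP table would contradict the decision taken at 6 mg/kg every 14 days. The documents do not support that. The SRC had already acted on 2 of 5 evaluable (Protocol 5.2.1.1), nothing directs anyone to enter the AE summary row in Figure 6, 33.3% remains above the 30% limit, and Figure 7 reads D either way.

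A reader might also take the Section 3.2 composite as the rule for every part. It is defined for the Part A mTPI-2 cohort (10 subjects, SAP 4.2); Section 3.6 sets two separate rates for Part C1.

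On the second gap, it is fair to say that subject-level listings carry the DLT flag, dates, relationship and action taken, and that ocular toxicity and neuropathy get profile tables with onset time and action taken. What is missing is a summary, not the data.

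**Conclusion.** The point holds as a reporting error on a primary objective and should be fixed. At 6 mg/kg every 14 days the SAP as written gives 33.3% where the protocol's population gives 40.0%. The table would then not match the figure on which the recorded decision rests, although that decision and the finding that the rate exceeds 30% are unaffected. The protocol's second monitored rate, with its 20% limit, has no summary table.

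This rests on three assumptions. The DLT row uses the safety population, as SAP 9.1 implies. The counts of 6 treated and 5 evaluable at 30 November 2019 are still current: SAP 4.2 gives 10 subjects in Part C1 with no split between 4 and 6 mg/kg, and 6 + 4 is consistent but not stated. The DLT-evaluable rule applies under the Module version the SAP cites (Amendment 06): the Module text reviewed is later, but the SAP itself uses the term evaluable for the mTPI-2 algorithm.

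**What to change.** In SAP Section 9, add a DLT-evaluable population with the definition in Protocol 3.1 and 9.1. In SAP 12.1, report DLTs on that population by dose and schedule, with the number treated shown alongside. Add a row, by dose and schedule, for treatment-related AEs leading to a missed dose or discontinuation within 42 days of first dose and, for the Part A mTPI-2 cohort, a row for the composite of that event or a DLT.

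The cost is SAP wording and one or two extra table rows. No new data collection is foreseen: the listings already hold the DLT flag, dates, relationship and action taken, and the recorded infusion dates can confirm a missed dose if the action-taken categories do not separate it. The one small downside is that some reported DLT rates become slightly higher.
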